2.3.4.1 Analysis of adverse events (AEs)

The number and percentage of subjects who had at least one serious adverse event, classification of serious adverse event, adverse events of special interest and classification of adverse events of special interest from study will be provided.

- All SAEs will be summarized by SOC and PT;

- All AESIs will be summarized by SOC and PT;

2.3.4.2 Clinical laboratory data analysis

Laboratory tests included blood sugar, prothrombin time, international standardized ratio, platelet count and serum creatinine.

For continuous laboratory parameters, summary statistics, including number of subjects, mean, standard deviation, median, minimum and maximum will be provided for observed values for each parameter.

If a lab test result is recorded as "<10", then it will be summarized as a value of "5", if applicable; and likewise, ">10" will be summarized as "10".

2.3.4.3 Analysis of vital signs

Summaries of vital signs parameters will be presented by treatment group, using summary statistics, including number of subjects, mean, standard deviation, median, minimum and maximum for observed values for each parameter.

2.3.4.4 Analysis of neuroimaging

ASPECTS (0-10) and change from baseline are continuous variables and will be presented with summary statistics. The frequency table of each point will also be provided by treatment groups.

Other results of CT and CTA will be summarized using frequency table by treatment groups (if necessary).

2.3.5 Analysis of quality of life

2.3.5.1 NIHSS score

NIHSS (0-42) score and change from baseline are continuous variables and will be presented with summary statistics, including number of subjects, mean, standard deviation, median, minimum and maximum, by treatment groups and by visits. Repeated measures of variance analysis will be used to explore the impact of treatment grouping visits and NIHSS baseline levels.

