1.3 STUDY OUTCOMES

Primary outcome:

The primary outcome is the score on the modified Rankin Scale (mRS) ([Table 1 in Appendix](#)) at 90 days (± 14 days). The mRS is the preferred disability parameter for clinical trials in stroke. The mRS is an ordinal hierarchical scale incorporating six categories from 0 up to and including 5, and describes the range of disability encountered post stroke. "Death" is assigned a score of 6. Assessment of outcome on the mRS will be performed by outcome committee, blinded to the allocated and actually received treatment. Their assessment will be based on standardized reports of a telephone interview by trained research personnel who are not aware of treatment allocation.

Secondary outcomes:

- Death within 90 days (± 14 days)

- Pre-interventional recanalization
- extended treatment in cerebral ischemia scale (eTICI) score on final angiography of IAT ([Table 2 in Appendix](#))
- Recanalization rate at 24-72 hours, assessed with CTA
- Score on the NIHSS at 24±6 hours and 5 -7 days. ([Table 3 in Appendix](#))
- Final infarct volume at 5-7 days. Final infarct volume will be assessed with the use of an automated, validated algorithm. Infarct size at day 5-7 will be compared with plain computed tomography (CT) and perfusion CT results (if available) at baseline.
- Dichotomized mRS of 0-1 vs. 2-6 at 90 days (±14 days)
- Dichotomized mRS of 0-2 vs. 3-6 at 90 days (±14 days)
- Dichotomized mRS of 0-3 vs. 4-6 at 90 days (±14 days)
- Score on the EuroQol-5 dimensions-5 level (EQ5D-5L) ([Table 4 in Appendix](#)) and Barthel index (BI) ([Table 5 in Appendix](#)) at 90 days (±14 days)

Safety outcomes:

- Hemorrhages according to the Heidelberg criteria [1]
- sICH scored according to the Heidelberg criteria [2]
- Embolization in new territory on angiography during IAT
- Occurrence of aneurysma spurium
- Occurrence of groin hematoma
- Infarction in new territory at 5-7 days ([Table 6 in Appendix](#))
- Death from all causes within 90 days (±14 days)

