1.5 STUDY PROCEDURES

Before starting the study, patients or their guardians must read and sign the informed consent approved by the current Ethics Committee (EC). All research steps should be carried out within the time window specified in the study protocol.

All patients will undergo assessment of the NIHSS at baseline, 24±6 hours and 5-7 days, which is routine in clinical procedure. It will be carried out by certified assessors. Patients will undergo NCCT and CTA at baseline. After 24-72 hours, CTA is repeated to determine recanalization. At 5-7 days, patients will undergo non-contrast computed tomography (NCCT) to assess infarct size.

In addition, this trial also makes use of "waste material": retrieved thrombi during intervention. These thrombi will be stored in the participating study centers for follow-up analysis.

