2.3.2 Analysis of efficacy outcomes

All efficacy data analyses will be based on ITT and for primary endpoint PPS will also be used.

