2.3.2.2 Secondary efficacy outcome

Continuous secondary efficacy outcomes are mainly infarct size at 5-7 days after operation and recanalization rate before intervention as well. Analysis for these outcomes will be mainly based on statistical descriptions. Where necessary, analysis of variance or corresponding non-parametric test will be used for between-group comparisons. If applicable, the linear regression analysis will be used with adjustment for the same covariate variables as the primary outcome analysis. When deemed necessary, log or other common transformation of non-normal distribution will be used.

Categorical secondary outcomes include mortality at 90 days after operation, recanalization rate at 24-72 hours, dichotomized mRS score at 90 days after operation (0-1 vs. 2-6, 0-2 vs. 3-6, 0-3 vs. 4-6), successful recanalization before and after Mechanical thrombectomy (MT), and eTICI score at MT final angiography. Chi-square test will be used for comparison between the two groups, or Fisher's exact test will be used for comparison when applicable. The categorical secondary outcomes will be analyzed by logistic or ordered regression analysis to provide a common odds ratio and its confidence interval, if applicable. The adjustment method is the same as that in the primary outcome analysis.

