2.4.2 Missing data

We will report proportions of missing values for all collected variables where needed.

Baseline characteristics missing data will be imputed by regression interpolation as appropriate.

If there is a large number of missing data on efficacy and safety, an evaluation on the missing data should be conducted before analysis, and will propose and determine the solution before database lock.

For patients who died within the study period, the worst scores will be assigned for all not-assessed clinical outcome measures in their analyses, as follows [Table 2](#).

Table 2 The worst scores of clinical outcomes

Clinical outcomes	The worst scores
mRS	6
NIHSS	42
The Barthel index	0

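### NIHSS is a listed outcome at 24 hours and at 5-7 days, but the SAP specifies no between-arm estimate at either time; it names only an exploratory repeated-measures ANOVA with unstated terms and contrast

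*SAP*

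**What the plan says.** SAP section 1.3 lists "Score on the NIHSS at 24±6 hours and 5 -7 days" among the secondary outcomes, and section 2.1.2.2 repeats it. Section 1.2 makes neurological recovery on the NIHSS part of the third objective, as a comparison between arms. On the schedule, section 1.5 says "All patients will undergo assessment of the NIHSS at baseline, 24±6 hours and 5-7 days".

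The analysis is in section 2.3.5.1, under quality of life. It plans descriptive statistics for the score and its change from baseline: "mean, standard deviation, median, minimum and maximum, by treatment groups and by visits". The one inferential sentence is "Repeated measures of variance analysis will be used to explore the impact of treatment grouping visits and NIHSS baseline levels". It gives no model terms, covariance structure, role for baseline, reported contrast or rule for an incomplete pair of visits.

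Three other sections bear on this:
- Section 2.3.2.2 says "Continuous secondary efficacy outcomes are mainly infarct size at 5-7 days after operation and recanalization rate before intervention as well". NIHSS is not named there, nor in the categorical list. For continuous secondary outcomes the section allows, conditionally, an ANOVA or non-parametric test, and says "the linear regression analysis will be used with adjustment for the same covariate variables as the primary outcome analysis" where applicable.
- Section 2.3.2 says "All efficacy data analyses will be based on ITT and for primary endpoint PPS will also be used".
- Section 2.4.2 says that for patients who died "the worst scores will be assigned for all not-assessed clinical outcome measures in their analyses", which for NIHSS is 42. For survivors it fixes no rule in advance. A solution is to be settled before database lock if many data are missing.

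**The concern.** Two time points are listed as outcomes, yet the plan does not commit to an arm difference with a confidence interval at either. The treatment effect most readily taken from a repeated-measures ANOVA is the main effect, which pools the visits. An early difference that fades by day 5-7, or one that appears late, would then be diluted, and neither listed outcome would have its own estimate.

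A classical repeated-measures ANOVA also uses only patients with both visits. A survivor without a day 5-7 score would lose the 24-hour score too. That costs precision, and it can bias the result if the missing later score is related to how the patient was doing at 24 hours.

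With the contrast unstated, the main effect, the interaction or a visit-specific result could be chosen after the data are seen. Section 1 says the SAP exists to predefine the methods before database lock.

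**Working it through.** **1. Inputs.** The SAP states no NIHSS effect, SD, correlation or missingness. The sample size comes from section 1.4 and is reproduced first: 710 × 0.85 = 603.5, and 603.5 / 0.95 = 635.3, which rounds up to 636, or 318 per arm. Evaluable patients per arm: 318 × 0.95 ≈ 302.

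Assumed: a 2-point difference at one visit and none at the other; SD 9 at each visit (range 7 to 12); correlation between visits ρ = 0.8 (range 0.5 to 0.9). No baseline adjustment is modelled.

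**2. What the main effect estimates.** With visit effects d1 and d2, it is (d1 + d2)/2. For effects of 2 and 0 this is 1.0, exactly half. This step needs no assumption about SD or correlation. A simulation of 2,000 trials gave 2.00 points at the affected visit and 1.01 averaged.

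**3. Power, two-sided 0.05.**
- One visit: SE = 9 × √(2/302) = 0.732; 2/0.732 = 2.73; power = Φ(2.73 − 1.96) = 78%.
- Two-visit mean: SD = 9 × √((1 + 0.8)/2) = 8.54; SE = 8.54 × √(2/302) = 0.695; 1/0.695 = 1.44; power = Φ(1.44 − 1.96) = 30%.

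| SD | ρ | Contrast at the affected visit | Averaged main effect |
|---|---|---|---|
| 9 | 0.5 | 78% | 35% |
| 9 | 0.8 | 78% | 30% |
| 9 | 0.9 | 78% | 29% |
| 7 | 0.8 | 94% | 46% |
| 12 | 0.8 | 54% | 19% |

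**4. The opposite case.** If both visits carry the same effect, the standardized main effect is the single-visit value times 1/√((1 + ρ)/2). That factor is 1.03 at ρ = 0.9 and 1.15 at ρ = 0.5, so averaging is then slightly better. With the effect at one visit only, the factor is 0.51 (ρ = 0.9) to 0.58 (ρ = 0.5).

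**5. A treatment-by-visit term.** Its contrast is d2 − d1, and the same simulation recovered 1.99 of 2 points. It would therefore reveal an effect confined to one visit. It does not estimate d1 or d2, however: two equal effects of 2 points give an interaction of 0. The visit-specific differences have to be requested from the model.

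**6. Incomplete pairs.** Assume missingness m per visit, independent between visits. Patients with both scores number 636(1 − m)²; those with at least one number 636(1 − m²).

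| m | Both visits | At least one visit |
|---|---|---|
| 2% | 611 | 636 |
| 5% | 574 | 634 |
| 10% | 515 | 630 |

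Patients who died are scored 42 under section 2.4.2 and do not drop out, so any such loss concerns survivors.

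**The case against.** The strongest reply is that the SAP does not specify the unfavourable model. Section 2.3.5.1 names treatment and visits as factors, and a treatment-by-visit term is a routine part of such an analysis. Nothing excludes it. Nor does anything exclude a likelihood-based fit, which keeps patients with one score. Section 2.3.2.2 describes its list of continuous outcomes only as the main ones and conditionally allows other tests and adjusted regression, so a comparison at each visit is not ruled out. The by-visit summaries also let a reader derive an unadjusted difference at each time. The power figures rest on assumed inputs and on an effect wholly absent at one visit.

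Most of this stands. A reader might infer that the plan averages the visits, deletes incomplete patients and so breaks the intention-to-treat rule of section 2.3.2. The document does not support that. Averaging follows only if the main effect is what is reported, and deletion only if a classical ANOVA is used; the SAP commits to neither. Section 2.2.1 defines the ITT population by randomisation and assigned group, and section 2.4.2 deals with missing data separately.

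What the reply does not supply is a stated estimate. An analysis that is merely permitted is not prespecified, and an interaction test does not give the arm difference at 24 hours or at 5-7 days.

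**Conclusion.** The point holds as under-specification, and it is minor. For an outcome listed at two times, the only inferential method named is an exploratory repeated-measures ANOVA with no between-arm contrast at either time.

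The halving of a one-visit effect is plain arithmetic, but it is conditional on the main effect being reported. The fall in power from 78% to about 30% (29% to 35% over the correlations tried at SD 9) is illustrative, because the effect, SD and correlation are assumed. With equal effects at both visits there is no loss. The loss of survivors with one score is conditional on a classical ANOVA, and its size depends on missingness that the SAP does not state.

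The outcome is secondary and its analysis exploratory. Neither the primary non-inferiority conclusion nor the sample size is affected.

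**What to change.** In SAP section 2.3.5.1, replace the inferential sentence with wording such as:

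> NIHSS will be analysed with a mixed model for repeated measures (unstructured covariance) containing treatment, visit, treatment-by-visit, baseline NIHSS and baseline-by-visit. Every randomised patient with at least one post-baseline score is included, counting scores assigned after death under section 2.4.2. The adjusted between-arm difference and its 95% CI will be reported at 24 hours and at 5-7 days.

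This settles the model, its terms, the contrast, the role of baseline and the handling of one missing visit. How deaths are scored is a separate matter and is left as it is.

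The cost is SAP wording and a mixed-model procedure (PROC MIXED) in SAS, the software already named in section 5. No new data are needed. The downside is two reported contrasts instead of one; the averaged effect remains available from the same model.

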2.3.5.2 EQ5D-5L score

The frequency and percentage of EQ5D-5L scale will be summarized according to each dimension. If necessary, Chi-square test will be used for comparison between the two groups, or Fisher's exact test will be used for comparison when applicable.

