1.5.1 Procedures

All the procedures to be recorded are listed in [Table 1](#).

Table 1 Procedures

Items	Procedures(includes but not limited to:)
Demography	Date of birth (based on valid identity documents), sex, age
Medical History	Disease history, smoking/alcohol drinking history, medications
Modified Rankin Scale	Disability level, ranging from 0~5
Glasgow coma Scale	Eye Opening, Best Verbal Response, Best Motor Response
Vital Signs	Systolic/diastolic blood pressure, heart rate, body temperature, height, weight
NIHSS	Level of consciousness (LOC), LOC Questions, LOC Commands, Best Gaze, Visual, Facial palsy, Motor arm, Motor leg, Limb ataxia, Sensory, Best language, Dysarthria, Extinction and Inattention
Laboratory tests	Serum glucose, Activated Partial Thromboplastin Time (APTT), International normalized ratio (INR), Thrombocyte count, Serum creatinine
eTICI	eTICI classification includes 0, 1, 2a, 2b, 2C and 3
EQ5D-5L score	Mobility, Self-Care, Usual-Activities, Pain/Discomfort, Anxiety/Depression
BARTHEL index	Feeding, Bathing, Grooming, dressing, Bowels, Bladder, Toilet use, Transfers(bed to chair and back), Mobility(on level surfaces), Stairs
Neuroimaging	CT, CTA, MRI and other imaging examinations

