2.1.2.2 Secondary efficacy variables

- Death within 90 days (± 14 days)
- Pre-interventional recanalization
- eTICI score on final angiography of IAT. ([Table 2 in Appendix](#))
- Recanalization rate at 24-72 hours, assessed with CTA
- Score on the NIHSS at 24 \pm 6 hours and 5 -7 days. ([Table 3 in Appendix](#))
- Final infarct volume at 5-7 days. Final infarct volume will be assessed with the use of an automated, validated algorithm. Infarct size at day 5-7 will be compared with plain CT and perfusion CT results (if available) at baseline.
- Dichotomized mRS of 0-1 vs. 2-6 at 90 days (± 14 days)
- Dichotomized mRS of 0-2 vs. 3-6 at 90 days (± 14 days)
- Dichotomized mRS of 0-3 vs. 4-6 at 90 days (± 14 days)
- Dichotomized mRS of 0-4 vs. 5-6 at 90 days (± 14 days)
- Dichotomized mRS of 0-5 vs. 6 at 90 days (± 14 days)

- Score on the EQ5D-5L and Barthel index at 90 days (± 14 days)

Pre-interventional recanalization: Recanalization rate (eTICI 2b, 2c or 3) before patients received mechanical intra-arterial treatment according to the DSA.

Recanalization rate at 24-72 hours: defined as the proportion of patients in whom recanalization as determined on 24-72 hours CTA is achieved.

eTICI score: eTICI assessment will be performed post IAT. The eTICI classification includes 0, 1, 2a, 2b, 2c and 3 ([Table 2 in Appendix](#)).

NIHSS score: The NIHSS is an ordinal hierarchical scale to evaluate the severity of stroke by assessing a patient's performance. Scores range from 0 to 42, with higher scores indicating a more severe deficit ([Table 3 in Appendix](#)). NIHSS assessment will be performed at baseline, 24 ± 6 hours post operation and 5-7 days post operation.

The EuroQoL 5-dimensions 5-level (EQ-5D-5L) questionnaire is a standardized measure of health outcome that has been used extensively in patients with stroke ([Table 5 in Appendix](#)). EQ5D-5L assessment will be performed at 90 ± 14 days post operation.

The Barthel index (BI) is an ordinal scale used to measure performance in 10 activities of daily living (ADL). Test scores range from 0 to 100, with higher scores indicating better performance in these daily activities ([Table 4 in Appendix](#)). BI assessment will be performed at 90 ± 14 days post operation.

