Appendix table 4 EUROQOL 5D-5L

The EuroQoL 5-dimensions 5-level (EQ-5D-5L) questionnaire is a standardized measure of health outcome that has been used extensively in patients with stroke.

Under each heading, please tick the ONE box that best describes your health TODAY.

Mobility

I have no problems in walking about

I have slight problems in walking about

I have moderate problems in walking about

I have severe problems in walking about

I am unable to walk about

Self-care

I have no problems washing or dressing myself

I have slight problems washing or dressing myself

I have moderate problems washing or dressing myself

I have severe problems washing or dressing myself

I am unable to wash or dress myself

Usual activities (e.g. work, study, housework, family or leisure activities)

I have no problems doing my usual activities

I have slight problems doing my usual activities

I have moderate problems doing my usual activities

I have severe problems doing my usual activities

I am unable to do my usual activities

Pain/discomfort

I have no pain or discomfort

I have slight pain or discomfort

I have moderate pain or discomfort

I have severe pain or discomfort

I have extreme pain or discomfort

Anxiety/depression

I am not anxious or depressed

I am slightly anxious or depressed

I am moderately anxious or depressed

I am severely anxious or depressed

I am extremely anxious or depressed

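### EQ5D-5L at 90 days: the only tests named ignore the order of the five levels, and neither the meaning of 'score' nor the handling of deaths is fixed

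*SAP*

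**What the plan says.** SAP 1.3 and 2.1.2.2 name the outcome as "Score on the EQ5D-5L and Barthel index at 90 days". Table 1 in 1.5.1 describes the content of the EQ5D-5L score as five dimensions: "Mobility, Self-Care, Usual-Activities, Pain/Discomfort, Anxiety/Depression". Appendix table 4 gives each dimension five ordered responses, from no problems, through entries such as "I have slight problems in walking about", to unable or extreme.

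The analysis is in 2.3.5.2: "The frequency and percentage of EQ5D-5L scale will be summarized according to each dimension". The arms are then compared as follows: "If necessary, Chi-square test will be used for comparison between the two groups, or Fisher's exact test will be used for comparison when applicable". No index, value set or sum score is defined in the SAP.

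Two other sections bear on the point. Section 2.3.2.2 says "The categorical secondary outcomes will be analyzed by logistic or ordered regression analysis to provide a common odds ratio", qualified by an 'if applicable', but its list of categorical outcomes does not include EQ5D-5L. For patients who died, 2.4.2 says that "the worst scores will be assigned for all not-assessed clinical outcome measures", but its Table 2 gives values only for mRS, NIHSS and the Barthel index.

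**The concern.** A chi-square or Fisher test on a table of two arms by five levels asks only whether the two distributions differ in any way. The result is the same if the level labels are shuffled. It therefore cannot say which arm has the better health status, and it spreads its sensitivity over 4 degrees of freedom when the question of interest, better or worse, needs one. The SAP handles its main ordered outcome, the mRS, with a proportional odds model and a common odds ratio (2.3.2.1), so EQ5D-5L gets weaker treatment than a tool already in the plan.

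Two choices are also left open. The condition 'if necessary' has no stated trigger, so the decision to test could be taken after the data are seen. And without a rule for deaths, the comparison may be restricted to survivors without saying so.

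**Working it through.** **Plan's own figures.** The SAP gives no effect size, level distribution or power target for EQ5D-5L. Its only sample size is for the mRS (1.4). That figure serves to check the proportional odds formula used below:

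N = 12(1.960 + 0.842)² / {[ln 1.163 − ln 0.8]² (1 − Σp̄³)}

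Here p̄ is the mean of the two arms' mRS proportions. With Σp̄³ = 0.035 this gives N = 94.19 / (0.1400 × 0.9647) = 697, against 710 stated, a difference within 2%. Then 710 × 0.85 = 603.5, and 603.5 / 0.95 = 635.3, so 636 in total or 318 per arm, as stated.

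**Inputs for the comparison.**
- Per arm: 318 (SAP 1.4), and 250 as an assumed number of assessed survivors. The planned control mortality of 21% gives 318 × 0.79 = 251.
- Two-sided alpha 0.05.
- Level distributions in the control arm are assumptions, in %: 20/20/20/20/20; 35/20/15/10/20; 60/20/10/6/4; 30/25/20/12/13; 50/25/15/6/4.
- Common odds ratios: 1.163, the SAP's assumed effect for the mRS, and 1.3 to 2.0 as assumptions.

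**Formulas.** With p and q the level proportions in the two arms and n the number per arm:
- Chi-square test: noncentrality λ = n Σ(p − q)²/(p + q), 4 df, critical value 9.488.
- Ordered test (proportional odds or Wilcoxon): V = (2n/12)(1 − Σp̄³), power ≈ Φ(ln OR · √V − 1.960).

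**One case in full.** Take the uniform distribution, OR 1.5 and n = 318. The shifted arm is 27.3/22.7/19.2/16.5/14.3%. For the chi-square test, λ = 8.27 and power is 62.1%. For the ordered test, V = 50.79, ln 1.5 × √50.79 = 2.890, and Φ(0.930) = 82.4%. The loss is 20.3 points. The two noncentralities are nearly equal (8.27 and 2.890² = 8.35), so almost all of the loss comes from using 4 df instead of 1. In general, 80% power on 1 df becomes 59.5% on 4 df at the same noncentrality.

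**Range over the five assumed distributions.**

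| n per arm | OR | Chi-square, % | Ordered test, % | Loss, points |
|---|---|---|---|---|
| 250 | 1.163 | 8.9–10.0 | 13.5–15.9 | 4.7–5.9 |
| 250 | 1.3 | 18.0–22.5 | 30.8–38.2 | 12.9–15.7 |
| 250 | 1.5 | 38.9–50.6 | 60.5–72.7 | 21.6–22.1 |
| 250 | 1.8 | 70.9–85.2 | 88.8–96.0 | 10.8–17.9 |
| 250 | 2.0 | 84.7–95.0 | 96.0–99.2 | 4.2–11.3 |
| 318 | 1.163 | 10.0–11.5 | 15.9–19.0 | 5.9–7.4 |
| 318 | 1.3 | 22.1–28.1 | 37.7–46.5 | 15.5–18.4 |
| 318 | 1.5 | 48.7–62.1 | 70.9–82.4 | 20.3–22.2 |
| 318 | 1.8 | 82.2–93.1 | 94.7–98.7 | 5.6–12.6 |
| 318 | 2.0 | 92.8–98.5 | 98.7–99.9 | 1.4–5.9 |

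Simulation (20,000 trials per setting, first three distributions, odds ratios up to 1.54) agrees with the formulas to within about one point. At OR 1 both tests reject in about 5%.

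**Direction.** Assume 35/20/15/10/20% in one arm and 40/15/10/10/25% in the other. A random patient from either arm is then equally likely to be better or worse than one from the other (probability index 0.500). Here λ = n × 0.0025 × (1/0.75 + 1/0.35 + 1/0.25 + 1/0.45) = 0.02603n, which is 6.51 at 250 and 8.28 at 318. The chi-square test rejects in 51% and 62% of trials, the rank test in 5%. This is not a false positive, since the distributions do differ, but the p-value says nothing about which arm does better.

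**The case against.** The strongest reply is that EQ5D-5L is one unpowered secondary outcome, that its analysis is descriptive first, and that 2.3.2.2 already contains an ordered model for categorical secondary outcomes. Its list is introduced as what these outcomes include, so EQ5D-5L might be covered. This stands in part: the SAP is ambiguous rather than closed to an ordered analysis. But the general provision is conditional and does not name EQ5D-5L, while the section written for EQ5D-5L names only chi-square and Fisher tests.

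Three stronger readings are tempting, and the documents do not support them.
- A reader might infer that the named outcome will have no result. It will: frequencies for every dimension are committed, they show direction by eye, and Table 1 in 1.5.1 uses 'score' for the five dimension responses. Section 2.1.4 plans no health economics, which also fits a profile. The gap is that the SAP never says which meaning applies.
- A reader might infer a flat loss of 20 points. That size appears only where an ordered test would have roughly 60 to 85% power. At the SAP's only stated effect both tests have under 20% power, and changing the test rescues little.
- A reader might infer that a uniform shift is the pattern the chi-square test detects worst. To the usual approximation its power depends only on the noncentrality, not on the pattern. It is weaker than an ordered test for shifts, but not specially blind to them.

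Replacing the profile by a single index is a choice, not a correction. An index needs a value set that the SAP does not supply and a rule for deaths that it does not give.

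**Conclusion.** The point holds as a weakness in the analysis of one secondary outcome. The tests named in 2.3.5.2 do not suit ordered five-level items. They give no estimate or direction, and they cost between about 1 and 22 points of power for a consistent shift, most at odds ratios near 1.4 to 1.5. These figures rest on assumed level distributions, proportional odds shifts and 250 to 318 assessed patients per arm. The mismatch between ordered items and unordered tests rests on no such assumption. The meaning of 'score' and the treatment of deaths are open in the text. The primary non-inferiority analysis of the mRS is not touched, and the change is worth making mainly because it is nearly free.

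**What to change.** In SAP 2.3.5.2:
- Replace the chi-square and Fisher tests by the proportional odds model of 2.3.2.1 with its planned covariates, and report a common odds ratio with 95% CI for each dimension. A Wilcoxon rank-sum test is an acceptable unadjusted alternative for the p-value, though it gives no odds ratio.
- Remove 'if necessary', or state before lock what triggers the comparison.
- State whether 'score' means the five-dimension profile or an index. If an index, name the value set before database lock.
- State how patients who died are handled, for example survivors only and labelled so, or death as a further worst category, and bring Table 2 in 2.4.2 into line.

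The cost is SAP wording and a few more model fits on data already collected. The downside is reliance on the proportional odds assumption, which should be checked for each dimension. Five dimension-wise results remain, so they should be read as a profile and not as five separate claims.
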